### **H 2.2 Chest X-rays**

Chest X-ray assessments will not be used for assessment of TLs. Chest X-rays can, however, be used to assess NTLs and to identify the presence of NLs. However, there is preference that a higher resolution modality, such as CT, be used to confirm the presence of NLs.

### **H 2.3 Plain X-ray**

Plain X-ray may be used as a method of assessment for bone NTLs and to identify the presence of new bone lesions.

## **H 2.4 Isotopic Bone Scan**

Bone lesions identified on an isotopic bone scan at baseline and confirmed by CT, MRI or X-ray at baseline should be recorded as NTLs and followed by the same method as per baseline assessment.

Isotopic bone scans may be used as a method of assessment to identify the presence of new bone lesions at follow-up visits. New lesions may be recorded in case positive hot-spots appear on a bone scan that were not present on a previous bone scan; however, a newly observed equivocal hot-spot on a bone scan that cannot be verified with correlative imaging (CT, MRI, or X-ray) of the same anatomical region shall not be the only trigger for a PD assessment at that time point.

## **H 2.5 FDG-PET**

F-Fluorodeoxyglucose positron emission tomography/CT scans may be used as a method for identifying NLs for RECIST 1.1 assessments according with the following algorithm: NLs will be recorded where there is positive F-Fluorodeoxyglucose uptake which is not present on the baseline or prior FDG-PET scan or when its location corresponds to NL on a companion CT/MRI that has been collected close in time to the FDG-PET scan. A positive FDG-PET scan lesion should be reported only when an uptake (eg, standardised uptake values) greater than twice that of the surrounding tissue or liver is observed. The PET portion of the PET/CT introduces additional data that may bias an investigator if it is not routinely or serially performed. Therefore, if there is no baseline or prior FDG-PET scan available for comparison, and no evidence of NLs on companion CT/MRI scans, then follow-up CT/MRI assessments should continue as per the regular imaging schedule to verify the unequivocal presence of NLs.

At present, low-dose or attenuation correction CT portions of a combined FDG-PET/CT scan are of limited use in anatomically based efficacy assessments, and it is therefore suggested that they should not substitute for dedicated diagnostic contrast-enhanced CT scans for tumour measurements by RECIST 1.1. In exceptional situations, if a site can document that the CT performed, as part of a PET/CT examination, is of identical diagnostic quality (with IV contrast) to a dedicated diagnostic CT scan, then the CT portion of the PET/CT can be used for RECIST 1.1 tumour assessments. Caution that this is not recommended because the PET portion of the CT introduces additional (PET) data that may bias an investigator if it is not routinely or serially recorded.

## **H 2.6 Ultrasound**

Ultrasound examination will not be used for RECIST 1.1 assessment of tumours as it is not a reproducible method (operator dependent), is subjective in interpretation, and may not provide an accurate assessment of the true tumour size. Tumours identified by ultrasound will need to

be assessed by correlative CT or MRI anatomical scan.

## **H 2.7 Other Tumour Assessments**

### **H 2.7.1 Clinical Examination**

Clinical examination of skin/surface lesions (by visual inspection or manual palpation) will not be used for RECIST 1.1 assessments. Tumours identified by clinical examination will need to be assessed by correlative CT or MRI anatomical scans.

### **H 2.7.2 Endoscopy and Laparoscopy**

Endoscopy and laparoscopy will not be used for tumour assessments as they are not validated in the context of tumour measurements.

### **H 2.7.3 Histology and Cytology**

Histology or tumour markers on tumour biopsy samples will not be used as part of the tumour response assessments per RECIST 1.1. Results of cytological examination for the neoplastic origin of any effusion (eg, ascites, pericardial effusion, and pleural effusion) that appears or worsens during the study will not be used as part of the tumour response assessment as per RECIST 1.1. Furthermore, an overall assessment of CR (all other disease disappears/reverts to normal) would be changed to PR if an effusion remains present radiologically.

## **H 2.8 Measurability of Tumour Lesions at Baseline**

### **H 2.8.1 RECIST 1.1 Measurable Lesions at Baseline**

A tumour lesion that can be accurately measured at baseline as  $\geq 10$  mm in the longest diameter for non-nodal lesions or  $\geq 15$  mm in short axis diameter for lymph node lesions with IV contrast-enhanced CT or MRI and that is suitable for accurate repeated measurements. The short axis is defined as the longest in-plane axis perpendicular to the long axis.

### **H 2.8.2 Non-measurable Lesions at Baseline**

- Truly non-measurable lesions include the following:
  - Bone lesions (see exception below for soft tissue component)
  - Leptomeningeal disease
  - Ascites, pleural effusion, or pericardial effusion
  - Inflammatory breast disease
  - Lymphangitic involvement of skin or lung
- All other lesions, including small lesions, ie, longest diameter  $< 10$  mm or pathological lymph nodes with  $\geq 10$ -mm to  $< 15$ -mm short axis diameter at baseline. Please note that

lymph nodes with < 10-mm short axis diameter are considered non-pathological and should not be recorded or followed as NTLs.

- Previously irradiated lesions. Localised post-radiation changes that affect lesion size may occur. Therefore, lesions that have been previously irradiated are typically considered non-measurable and as assessed as NTL.
- Brain metastases should be assessed as NTLs.

### **H 2.8.3 Special Considerations Regarding Lesion Measurability at Baseline**

- Bone lesions
  - Bone scan, PET scan, or plain X-ray are not considered adequate imaging techniques to measure bone lesions; however, these techniques can be used to confirm the presence or disappearance of bone lesions.
  - Lytic bone lesions or mixed lytic-blastic lesions, with identifiable soft tissue components, can be considered measurable if the soft tissue component meets the definition of measurability.
  - Blastic lesions are considered non-measurable.
- Cystic lesions thought to represent cystic metastases can be considered measurable lesions if they meet the criteria for measurability from a radiological point of view, but if non-cystic lesions are present in the same patient, these should be selected over cystic lesions as TLs.

### **H 2.8.4 RECIST 1.1 TL Selection at Baseline**

A maximum of 5 measurable lesions, with a maximum of 2 lesions per organ (including lymph nodes collectively considered as a single organ), representative of all lesions involved, should be identified as TLs at baseline. Target lesions should be selected on the basis of their size (longest diameter for non-nodal lesions or short axis for nodal lesions), but in addition should be those that lend themselves to reproducible repeated measurements. It may be the case that, on occasion, the largest lesion does not lend itself to reproducible measurement, in which circumstance the next largest lesion that can be measured reproducibly, should be selected.

Lymph nodes, in any location (local/regional and distant), are collectively considered as a single organ, with a maximum of 2 lymph nodes as TLs. A bilateral organ (eg, adrenal glands), a segmented organ (eg, liver), or a multilobed organ (eg, lung) is each considered as a single organ.

The site and location of each TL should be documented as well as the longest axis diameter for non-nodal lesions (or short axis diameter for lymph nodes). All measurements should be

recorded in whole (integer) millimetres and calculated values should be rounded to whole numbers. At baseline, the sum of the diameters for all TLs will be calculated and reported as the baseline sum of diameters. At follow-up visits, the sum of diameters for all TLs will be calculated and reported as the follow-up sum of diameters.

#### **Special Cases for TL Assessment at Baseline:**

- For TLs measurable in 2 or 3 dimensions, always report the longest diameter. For pathological lymph nodes measurable in 2 or 3 dimensions, always report the short axis diameter.
- When lymph nodes are coalesced and no longer separable in a conglomerate mass, the maximal short axis diameter of the coalesced mass should be recorded. Non-nodal lesions that coalesce should similarly be assessed by the longest axis diameter.
- Tumour lesions selected for fresh screening biopsy or FNA FFPE cell block should not be selected as TLs, unless imaging occurred at least approximately 2 weeks after biopsy, allowing time for healing.
- If the CT/MRI slice thickness used is  $> 5$  mm, the minimum size of measurable disease at baseline should be twice the slice thickness of the baseline scan.
- If a lesion has completely disappeared, the longest diameter should be recorded as 0 mm. If a lesion appears in the same location on a subsequent scan, it will be recorded as a NL.

#### **H 2.8.5 RECIST 1.1 NTL Selection at Baseline**

All other lesions, including non-measurable lesions and surplus measurable lesions, not recorded as TLs should be identified as NTLs at baseline. Measurements of these lesions are not required, but the presence or absence of each should be noted throughout follow-up.

### **H 2.9 Evaluation of Tumour Response and Progression**

#### **H 2.9.1 RECIST 1.1 TL Assessment at Follow-up**

This section defines the criteria used to determine objective tumour visit response for RECIST 1.1-defined TLs. The imaging modality, location, and scan date of each TL identified previously at baseline should be documented at follow-up visits with the long axis diameter for non-nodal lesions or short axis diameter for lymph node lesions. All measurements should be recorded in whole millimetres. The sum of the diameters for all TLs at each follow-up visit will be compared to the baseline sum of diameters (for response or SD) or to the smallest prior (nadir) sum of diameters (for progression).

### Special Cases for TL Assessment at Follow-up

- If a lesion has completely disappeared, the diameter should be recorded as 0 mm. If a lesion appears in the same location on a subsequent scan, it will be recorded as an NL.
- If a TL splits into 2 or more parts, the sum of the diameters of those parts should be recorded.
- If 2 or more TLs merge, then the sum of the diameters of the combined lesion should be recorded for one of the lesions and 0 mm recorded for the other lesion(s). If the merged TLs are non-nodal lesions, record the long axis diameter of the merged lesion. If pathologic lymph nodes coalesce and are no longer individually separable within a conglomerate mass, the maximal short axis diameter is recorded.
- If a TL is believed to be present and is faintly seen but too small to measure, a default value of 5 mm should be assigned. If an accurate measure can be given, this should be recorded, even if it is below 5 mm.
- If a TL cannot be measured accurately due to it being too large, provide an estimate of the size of the lesion. The choice of “Too large to measure” in the case report form will trigger an overall visit response of PD.
- When a TL has had an unscheduled, non-protocol intervention, the following apply:
  - Target lesion intervention may include radiotherapy, embolisation, excisional biopsy, surgery, etc, that is not a part of study intervention and might adversely affect the size of that TL
  - If an Intervention on a TL is ticked in the CRF, the diameter of the lesion is still recorded (0 mm if no longer present) and is included in the sum of diameters.
  - If a TL Intervention is ticked, the intervention must be reported for all subsequent assessments of that TL.
  - If a TL has an Intervention, the only overall visit responses allowed to be recorded by the investigator are NE or PD, with PD if the sum of diameters exceeds a 20% increase and at least a 5 mm absolute increase in the visit sum of diameters compared to the previous minimum (nadir) sum of diameters.
  - No visit with a recorded Target lesion intervention can be used as the minimum (nadir) sum of diameters.

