## **7 DISCONTINUATION OF STUDY INTERVENTION AND PATIENT DISCONTINUATION/WITHDRAWAL**

### **7.1 Discontinuation of Study Intervention**

It may be necessary for a patient to permanently discontinue (definitive discontinuation) study intervention. If study intervention is permanently discontinued, the patient will remain in the study to be evaluated for survival.

Patients may be discontinued from study intervention in the following situations. Note that discontinuation from study intervention is NOT the same thing as a withdrawal from the study.

- Patient decision. The patient is at any time free to discontinue treatment, without prejudice to further treatment.
- Adverse events.
- Severe non-compliance with the CSP.
- Disease progression as per RECIST 1.1; unless the patient is randomised to savolitinib plus placebo, when cross-over to savolitinib plus osimertinib may be permitted.

- Patients incorrectly initiated on study medication.
- Pregnancy.
- Specific stopping criteria, ie, ILD, acute anaphylaxis or QTcF interval prolongation with signs/symptoms of serious arrhythmia.

See the SoAs ([Table 1](#) and [Table 2](#)) for data to be collected at the time of intervention discontinuation and follow-up and for any further evaluations that need to be completed.

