**Table H2      RECIST Evaluation of Target Lesions**

Complete response (CR)	Disappearance of all TLs since baseline. Any pathological lymph nodes selected as TLs must have a reduction in short axis diameter to < 10 mm.
Partial response (PR)	At least a 30% decrease in the sum of diameters of TLs, taking as reference the baseline sum of diameters.
Stable disease (SD)	Neither sufficient decrease in the sum of diameters to qualify for PR nor sufficient increase to qualify for PD.
Progression of disease (PD)	At least a 20% increase in the sum of diameters of TLs, taking as reference the smallest previous sum of diameters (nadir)—This includes the baseline sum if that is the smallest on study. In addition to the relative increase of 20%, the sum must demonstrate an absolute increase of at least 5 mm from nadir.
Not evaluable (NE)	Only relevant if any of the TLs at follow-up were not assessed or NE (eg missing anatomy) or had a lesion intervention at this visit. Note: If the sum of diameters meets the PD criteria, PD overrides NE as a TL response.
Not applicable (NA)	Only relevant if no TLs present at baseline.

CR = Complete response; NA = Not applicable; NE = Not evaluable; PD = Progression of disease; PR = Partial response; RECIST = Response Evaluation Criteria in Solid Tumours; SD = Stable disease; TL = Target lesion.

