### H 2.9.3      RECIST 1.1 NL Identification at Follow-up

Details, including the imaging modality, the date of scan, and the location of any NLs will also be recorded in the CRF. The presence of one or more NLs is assessed as progression. The finding of an NL should be unequivocal, ie, not attributable to differences in scanning technique, change in imaging modality or findings thought to represent something other than tumour. If an NL is equivocal, for example because of its small size, the treatment and tumour assessments should be continued until the previously (pre-existing) new lesion has been assessed as unequivocal at a follow-up visit, and then the progression date should be declared using the date of the initial scan when the NL first appeared.

A lesion identified at a follow-up assessment in an anatomical location that was not scanned at baseline is considered an NL and will indicate PD.

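### A target lesion coded 0 mm and later seen again counts as a new lesion, so PD can be dated while the sum of diameters still meets PR and is not PD under Table H2

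*Supplement*

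**What the plan says.** The rule appears twice in Appendix H. The special cases for target lesions at follow-up (H 2.9.1) state "If a lesion appears in the same location on a subsequent scan, it will be recorded as an NL". The special cases at baseline (H 2.8.4) carry the same instruction: "If a lesion appears in the same location on a subsequent scan, it will be recorded as a NL". Neither sets a minimum size or a condition on the patient's overall response.

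H 2.9.3 gives the consequence: "The presence of one or more NLs is assessed as progression". Table H4 agrees, giving overall PD for a new lesion whatever the target and non-target status.

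For regrowth of target lesions, Table H2 has a separate test: a rise of at least 20% over the smallest previous sum and, in addition, "the sum must demonstrate an absolute increase of at least 5 mm from nadir". PR needs "At least a 30% decrease in the sum of diameters of TLs, taking as reference the baseline sum of diameters".

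Two other provisions bear on the case.
- H 2.9.3 asks that a new lesion be unequivocal: "If an NL is equivocal, for example because of its small size, the treatment and tumour assessments should be continued". Section 8.1.1 likewise advises continuing and reassessing when a new lesion is in doubt. Once the lesion is confirmed, "the progression date should be declared using the date of the initial scan when the NL first appeared".
- H 2.9.1 gives a target lesion that is faintly visible but too small to measure a default of 5 mm, which stays in the sum. It does not say whether this or the reappearance bullet governs a lesion previously coded 0 mm.

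Under Section 9.4.2, visit responses are assigned programmatically from the investigator's data. The resulting PD date is the PFS event and the end of response (Section 9.4.2.2).

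**The concern.** A lesion on the baseline target list is not new disease in the ordinary sense, and the plan already has a criterion for its regrowth. The reappearance bullet replaces that criterion with mere visibility. PD can then be dated in a patient whose measured burden still meets PR, has not risen by the required amount, or is still falling.

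PFS and DoR are at stake. Section 9.4.2.2 describes a stratified log-rank test and a hazard ratio for PFS, while DoR is summarised without a formal comparison. A PD call also has effects that later analysis cannot easily undo. It permits unblinding and cross-over (Sections 4.1.1 and 6.3), and scheduled RECIST imaging runs only to objective progression (Table 1) and is not required after cross-over on PD (Section 8.1.1).

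**Working it through.** The plan states no figure on this point, so the check applies Tables H2 and H4 to worked lesion sizes. Non-target disease is taken as not PD, with no other new lesion.

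**1. Regrowth needed for PD by the sum.** If the other lesions are unchanged, Table H2 needs regrowth of max(5 mm, 0.20 × nadir): 5 mm for a nadir up to 25 mm, 6 mm at 30 mm, 8 mm at 40 mm and 12 mm at 60 mm. The reappearance bullet needs none.

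**2. Worked cases (mm).** The last target lesion in each sum is the one that vanishes and returns. The right-hand column assumes the finding is judged unequivocal, then or later.

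| Case | Baseline | Nadir | Re-seen visit | Change from baseline | Change from nadir | By sum (H2) | As new lesion |
|---|---|---|---|---|---|---|---|
| A | 60+20 = 80 | 30+0 = 30 | 30+4 = 34 | −57.5% | +13.3%, +4 | PR | PD |
| B | 40+30+15 = 85 | 20+12+0 = 32 | 20+12+6 = 38 | −55.3% | +18.8%, +6 | PR | PD |
| C | 60+20 = 80 | 58+0 = 58 | 45+4 = 49 | −38.8% | −15.5%, −9 | PR, first time | PD |
| D | 60+10 = 70 | 60+0 = 60 | 60+4 = 64 | −8.6% | +6.7%, +4 | SD | PD |
| E | 40+20 = 60 | 20+0 = 20 | 20+5 = 25 | −58.3% | +25.0%, +5 | PD | PD |

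- In A and B a responder is called PD while the sum meets PR and fails the regrowth test.
- In C the sum is still falling. The patient was SD at the previous scan (58/80 = −27.5%) and would first reach PR at the visit called PD.
- D shows that a patient with SD can be caught too.
- In E both rules agree, so the conflict is limited to regrowth below the Table H2 threshold.

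**3. The two bullets of H 2.9.1.** If the returning lesion in case A is entered at the 5 mm default, the sum is 30 + 5 = 35 mm: 35/30 = +16.7% from nadir and 35/80 = −56.2% from baseline. That is PR. Recorded as a new lesion, the same scan is PD.

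**4. Timing.** Deferral under H 2.9.3 delays the call but not the date, because a confirmed lesion is back-dated. If Table H2 would have been met one scan later, the event is dated 6 weeks earlier (scans to week 24) or 8 weeks earlier (thereafter), within the scan windows.

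**5. Number affected.** The documents give no frequency. Assume that a share f of 5% to 20% of responders has a target lesion that vanishes and returns, with the originally planned 28 per arm (Section 9.2). The expected number per arm is 28 × ORR × f. The illustrative rates are the 30% in Section 4.2.1 and two rates used in Section 9.5.

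| ORR | f = 5% | f = 20% |
|---|---|---|
| 10% | 0.14 | 0.56 |
| 30% | 0.42 | 1.68 |
| 43% | 0.60 | 2.41 |

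These counts omit patients with SD such as case D. They are also too high for the actual trial, which stopped recruiting before reaching 56.

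**The case against.** The strongest reply is that the bullet does not act alone. H 2.9.3 and Section 8.1.1 require an unequivocal lesion, and H 2.9.3 names small size as a ground for waiting. A 4 or 5 mm lesion is the kind most likely to be deferred. This stands: it would be wrong to say that any reappearance of any size is PD on the spot. But the test is about certainty that the lesion is tumour, not about growth. A small lesion at a known tumour site may become certain without the sum rising 20% and 5 mm, and back-dating then applies.

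Second, a reader might infer a bias against the combination, since deeper responses expose more patients to the rule. With the same f in both arms, rates of 30% and 10% would put 30/(30+10) = 75% of affected responders in the combination arm. But f and the arm rates are assumptions, and case D shows that response is not the trigger. The documents do not establish a directional bias.

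Third, a reader might infer damage to the primary endpoint. Section 9.4.2.1 counts data up to progression, so a PR recorded earlier stands; only a pattern like case C loses a responder.

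Fourth, a reader might infer that combination patients are forced off treatment. Section 7.1 does list "Disease progression as per RECIST 1.1; unless the patient is randomised to savolitinib plus placebo" among the situations, but says only that patients may be discontinued. Section 4.1.1 lets combination patients continue past PD while they benefit.

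Finally, the rule is explicit, the same in both arms, and could be read as a deliberate special case. PFS by blinded independent review is a planned sensitivity analysis. However, H 1 ties only investigator assessments to this appendix, the review charter is not shown, and scans missing after a site PD call limit that check.

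**Conclusion.** The point holds in a limited form. The text allows a PD date that conflicts with the plan's own target-lesion criterion, and that date feeds PFS and DoR. Patients with at least one vanished target lesion are exposed: more often deep responders, but also some with SD. Any effect on ORR is confined to PR first reached at or after the visit in question.

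The size is probably a few patients at most. That rests on the assumed 5% to 20% of responders; neither the frequency nor any difference between arms can be derived from the documents. In a trial this small, one or two shifted events can still be visible in a PFS curve, so the derivation should be settled in advance. It should be corrected, but it does not threaten the primary analysis. The SAP is not shown and may already address it.

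**What to change.** Make the change in the analysis derivation only, in the SAP, which Section 9.4 says is finalised before unblinding.

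- In the programmatic visit response (Section 9.4.2), return a re-seen target lesion to the sum of diameters and judge the visit by Table H2. Treat reappearance as progression outright only after an overall CR. That exception is a convention the SAP must state, as it is not in the documents. It fits Table H2 where the nadir is 0 mm, since regrowth of 5 mm then already meets the absolute criterion.
- Report PFS and DoR on this basis, with the version that follows the new-lesion rule as a sensitivity analysis.
- Put the same rule in the independent review charter.
- Reconcile the reappearance bullets (H 2.8.4 and H 2.9.1) with the 5 mm default bullet, the unequivocal test in H 2.9.3 and Table H2.
- Leave site decisions on cross-over and treatment as they are.

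The cost is a short derivation rule and some data cleaning. H 2.9.3 names modality, date and location for a new lesion but not a diameter, so that measurement may need a query. PD will be dated later in a few patients. Some who have already crossed over or stopped scheduled scans after a site PD call may lack later scans and need censoring. That censoring may be informative, which is a further reason to show the new-lesion version alongside.
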